#### **1.1.14. Comprehensive Metabolic Panel/Complete Blood Count**

Blood will be drawn for a comprehensive metabolic panel and complete drug count during the medical screening to assess for participant safety. The total blood volume to be collected is approximately 8 mL. Additional laboratory samples may be taken at the discretion of the study physician if the results of any tests fall outside reference ranges or clinical symptoms necessitate testing to ensure safety.

#### **1.1.15. Concomitant Medications**

All medications taken by the participant 2-weeks prior to the start of screening and through the final visit, collected via participant self-report will be recorded on a source document and later entered electronically.

#### **1.1.16. Electrocardiogram (EKG)**

A 12-lead resting EKG will be obtained at the medical screening visit to assess for medical safety. Any abnormalities will be noted and an assessment of clinical significance will be made by the study physician.

#### **1.1.17. Medical History**

A Medical History interview will be conducted by the study physician at the medical screening visit and will screen for medical conditions that would make participation unsafe.

#### **1.1.18. Physical Exam**

A physical examination of the oral cavity, head, eyes, ears, nose, and throat, cardiovascular system, lungs, abdomen, extremities, skin, neuropsychiatric mental status and sensory/motor status, musculoskeletal system and general appearance will be performed during the medical screening visit.

#### **1.1.19. Urine Ethyl Glucuronide Test (EtG)**

The ethyl glucuronide (EtG) test is widely used to detect the presence in the urine of ethyl glucuronide, a breakdown product of ethanol, the intoxicating agent in alcohol. A urine EtG test will be conducted during the practice quit attempt on day 8 and day 14 to assess for recent alcohol use.

#### **1.1.20. Urine Drug Screen**

An FDA cleared, CLIA waived urine drug test card will be used at all visits to assess for recent use of opioids, cocaine, amphetamines, methamphetamine, THC, buprenorphine, methadone or benzodiazepines. Subjects must be negative for all substances except THC. Results will be recorded on the visit checklist first and then entered into the database.

### **1.1.21. Urine Pregnancy Test**

An FDA approved rapid result urine pregnancy test will be used (i.e., dipstick test) to assess for pregnancy in female participants at each screening visit and on Day 1 and Day 14 of the medication phase. If applicable, participants will be asked to sign a release of information form for study personnel to access medical records to obtain information regarding the outcome of a pregnancy that occurred during the study.

### **1.1.22. Vital Signs**

Vital signs include sitting blood pressure, pulse rate (after sitting for at least 3 minutes) and weight. Values will be recorded on the visit checklist and entered into the database. Vital signs will be collected at every in-person visit.

### **1.1.23. Alcohol Purchase Task (APT)**

The Alcohol Purchase Task (APT) will be used to assess state-level alcohol demand during the behavioral economics paradigm at Day 14. The APT is a hypothetical assessment wherein participants report how many standard drinks they would immediately consume at 17 price points: free, 5¢, 10¢, 25¢, 50¢, \$1, \$1.50, \$2, \$3, \$4, \$5, \$6, \$8, \$10, \$15, \$20, and \$30. A hypothetical APT will be used given evidence that derived alcohol demand indices correlate with both self-reported drinking measures and alcohol consumption during actual purchase tasks.

### **1.1.24. Alcohol Urge Questionnaire (AUQ)**

The Alcohol Urge Questionnaire (AUQ) is comprised of eight items rated on a 7-point Likert scale with items related to the subjective experience of alcohol craving. The AUQ has demonstrated high reliability in experimental studies of state alcohol craving and will be completed after every 3 minutes of exposure during the cue exposure paradigm on Days 1 and 14.

### **1.1.25. Daily Diary Assessment (DDA)**

Participants will complete daily diary assessments reporting on their mood, alcohol and cigarette craving, motivation to change, self-efficacy, pain, and drinking behavior from the previous day. Participants will complete the DDA electronically during the practice quit attempt (days 8-14). Research staff will distribute the link to the online daily diary assessment during each in-person and virtual visit.

### **1.1.26. Multiple Choice Procedure (MCP)**

The Multiple Choice Procedure (MCP) is the primary behavioral economic measure. The multiple-choice protocol consists of choices between immediate alcohol (a single standard-sized drink of the participant's preferred alcoholic beverage, available today) and 17 delayed monetary reward amounts (1¢, 5¢, 10¢, 25¢, 50¢, \$1, \$1.50, \$2, \$3, \$4, \$5, \$6, \$8, \$10, \$15, \$20, and \$30, available after one week). Participants will receive one randomly selected choice from the multiple-choice protocol. Participants will select a poker chip from a bowl containing chips pertaining to all of their choices on the multiple-choice protocol. A computerized random number generator program may be used in lieu of the poker chips if COVID safety regulations

require. If the participant's choice on that item is for alcohol, they will receive one standard drink at that moment. If their choice is for the delayed money, they will receive the money in cash after one week. All participants will remain in their respective visit room for a 15-minute consumption period. Participants who receive alcohol are permitted to consume their beverage during this time. This will be followed by a recovery period in a laboratory lounge.

#### **1.1.27. Profile of Mood States (POMS)**

The POMS measures dimensions of mood and will be completed during the cue reactivity sessions.

### **2. SAFETY MONITORING PLAN**

Safety monitoring will be conducted throughout the study; therefore, safety concerns will be identified by continuous review of the data by the PI and study physician, internal quality assurance checks, and DSMB.

#### **2.1. PI and Study Physician Safety Monitoring**

Participants will be given a 24-hour telephone number for calling the physician to discuss side effects, and physician office hours will be available as needed. Adverse events, including signs of sickness will be collected in an open-ended way at each in-person and phone study visit. Vital signs will be monitored at multiple time points during the experimental study visits. Alcohol withdrawal will be monitored at each visit through administration of the CIWA, and any significant withdrawal, as indicated by a score of 10+ on the CIWA will be reported to the study physician immediately. In the event that significant medical problems are encountered, the study blind will be broken and appropriate medical treatment will be provided.

#### **2.2. Internal Quality Assurance Monitoring**

The PI will designate appropriately qualified personnel to periodically perform quality assurance checks at mutually convenient times during and after the study. These monitoring visits provide the opportunity to evaluate the progress of the study and to obtain information about potential problems. The monitor will assure that data are accurate and in agreement with any paper source documentation used, verify that subjects' consent for study participation has been properly obtained and documented, confirm that research subjects entered into the study meet inclusion and exclusion criteria, verify that study procedures are being conducted according to the protocol guidelines, monitor review AEs and SAEs, and assure that all essential documentation required by Good Clinical Practices (GCP) guidelines are appropriately filed. At the end of the study, they will confirm that the site has the appropriate essential documents on file, and advise on storage of study records.

### **3. STATISTICAL METHODS AND POWER CONSIDERATIONS**

#### **3.1. Statistical Power**

Power analyses were conducted using G\*Power 3.1.9.2. In order to conduct a one-way ANOVA with fixed effects, we estimated a medium-to-large effect size ( $f=0.40$  and an alpha error probability of 0.05). Specifically, with 3 groups a sample size of 90 completers, the proposed

study has an actual power of 0.91%. Therefore, we propose to randomize 108 individuals (36 in each group) to reach a final sample of 30 completers per group. This will allow us the statistical power to detect a medium-to-large effect size as projected.

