## 4. STUDY DESIGN

### 4.1. Design Overview

This study design consists of a randomized, double-blind, placebo-controlled, 3-arm, parallel-group study of naltrexone (50 mg QD) and varenicline (1 mg BID). A total of 108 men and women with current AUD (moderate or severe) and reporting intrinsic motivation to change their drinking, will be randomly assigned to receive naltrexone (50 mg QD), varenicline (1 mg BID) or matched placebo. Post-randomization, all participants will complete an alcohol cue-reactivity paradigm prior to the initial dose of study medication. After a week-long medication titration period, participants will be asked to come in to the laboratory to receive their second medication blister pack and to begin a 7-day practice quit attempt, during which they will have daily virtual (online and phone) visits where they will report on their alcohol use. Additionally, a second cue-reactivity paradigm will be conducted 90 minutes after study drug administration, followed by a behavioral economics paradigm on the final day of the practice quit attempt (Day 14).

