### **1.1.6. Timeline Follow Back (TLFB)**

The Time Line Follow Back will be administered to assess quantity and frequency of alcohol, cigarette and marijuana use and will be completed at the initial screening (for the 30 days prior to that visit) and at each subsequent visit, including phone visits, to gather data for every day prior to and including the last visit. Information obtained in this interview will be recorded on the TLFB Calendar and transcribed to the database.

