#### **3.2.1. Primary Aim 1: To test that NTX and VAR will reduce drinking during the practice quit attempt as compared to placebo.**

A series of repeated measures ANCOVAs will be conducted using PROC GLM in SAS Statistical Software. Specifically, we will conduct repeated measures ANCOVAs on Percent Days Abstinent (PDA), and Drinks per Drinking Day (DPDD), our two co-primary outcomes, as predicted by Medication (NTX vs. PLAC and VAR vs. PLAC) a between-subjects factor and the covariate of baseline PDA and DPDD.

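### With no analysis population or missing-data method stated, completers-only is the implied default for Aims 1 and 2, and dropout that differs by arm could bias the drug-placebo contrasts

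*Combined protocol and SAP*

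**What the plan says.** Statistical Power sizes the trial "with 3 groups a sample size of 90 completers" and randomises 108, 36 per arm, "to reach a final sample of 30 completers per group". Completers are the only sample that the statistics section names, and it does not define the term.

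For Primary Aim 1 the Data Analytic Plan states: "A series of repeated measures ANCOVAs will be conducted using PROC GLM in SAS Statistical Software". The outcomes are PDA and DPDD, adjusted for their baseline values. Primary Aim 2 uses repeated measures ANOVA on the alcohol-minus-water craving score (AUQ), measured on Days 1 and 14. Nothing in the Data Analytic Plan says who is analysed, how missing data are handled, or what sensitivity analysis addresses dropout.

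The Timeline Follow Back (TLFB) section collects drinking at each visit, including phone visits, "to gather data for every day prior to and including the last visit". The compensation section lets participants stop at any time, and no outcome follow-up after stopping is described. The nearest thing to a completion rule is attendance at 7 of 8 visits, which governs only the payment bonus.

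**The concern.** Repeated measures analysis in PROC GLM, in its usual layout of one row per participant, removes anyone missing one of the repeated values or the covariate. With nothing in the plan to counter this, an analyst would by default compare those with complete data.

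In a quit attempt, being missing is plausibly related to the outcome:

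- The breathalyzer section requires a zero reading before any assessment, so someone who has been drinking on Day 8 or Day 14 cannot be assessed then. Rescheduling is described only for the screening visits.
- Anyone who leaves during the titration week has no quit-week outcome.
- Anyone who leaves before Day 14 has no on-drug craving score for Aim 2.
- The background sections say that varenicline may strengthen the aversive effects of alcohol and that adherence to oral naltrexone is poor. Reasons for leaving could therefore differ by arm. This is plausibility, not evidence.

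An arm that loses more of its drinkers would show a higher PDA among those who remain. The trial is meant to support go/no-go decisions, so a false signal in either direction matters.

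**Working it through.** **Plan's own figures.** The inputs are 3 groups, f = 0.40, alpha 0.05 and N = 90, for a one-way ANOVA. The noncentrality is f² × N = 0.16 × 90 = 14.4 on 2 and 87 degrees of freedom, which gives power 0.926. The plan states "study has an actual power of 0.91" (printed with a percent sign). The two agree within 2 percentage points. The planned loss is 108 − 90 = 18, or 18/108 = 16.7%, which is 6 of 36 per arm. No dropout rate is stated.

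**Bias on the PDA scale.** In one arm, the completer mean minus the mean of all randomised equals p × g, where p is the dropout share and g is completer PDA minus dropout PDA. The bias in the contrast between arms A and B is p_A × g_A − p_B × g_B. The documents give neither p by arm nor g, so the values below are assumptions.

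| Dropout A v B | Gap A, B (points) | Bias (PDA points) |
|---|---|---|
| 23.3% v 10% (mean 16.7%) | 20, 20 | 0.133 × 20 = 2.7 |
| 23.3% v 10% | 30, 30 | 0.133 × 30 = 4.0 |
| 23.3% v 10% | 40, 40 | 0.133 × 40 = 5.3 |
| 16.7% v 16.7% | equal | 0 |
| 16.7% v 16.7% | 40, 20 | 0.167 × 20 = 3.3 |

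One day in seven is 14.3 points, so 2.7 to 5.3 points is 0.19 to 0.37 of a day. The last two rows show that equal counts remove the bias only if the gap is also equal.

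**A second model, in SD units of drinking.** Assume that dropout is correlated rho with drinking. The mean of those who remain then shifts by −rho × φ(z)/(1 − p), where z is the (1 − p) quantile of the standard normal distribution.

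| Dropouts (of 36 per arm) | rho 0.3 | rho 0.5 | rho 0.8 |
|---|---|---|---|
| 6 v 6, same mechanism | 0 | 0 | 0 |
| 6 v 6, drinking-related in one arm only | 0.09 | 0.15 | 0.24 |
| 12 placebo v 3 active | 0.11 | 0.19 | 0.30 |

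The 12 v 3 pattern works against the active drug. Reversing the counts gives the same size in its favour. For scale, f = 0.40 with both active arms equal corresponds to d = 0.85 against placebo. With no true effect, the rho 0.5 biases of 0.15 SD (30 v 30 remaining) and 0.19 SD (24 v 33 remaining) raise the two-sided 5% error of one pairwise test to about 9% and 11%.

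**Effect of the fix on power, same ANOVA.** With outcomes for all 108 and f = 0.40, power is 0.965. If the 18 dropouts are kept but show no effect, f falls to 0.40 × 5/6 = 0.333 and power is 0.873. The figure for 90 completers is 0.926.

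**The case against.** The strongest reply is that the quoted phrase is a recruitment target with a dropout allowance. That is correct. A reader might infer that the protocol defines its analysis set as completers and excludes everyone else. It does not: no sentence excludes non-completers, and no sentence includes all randomised participants.

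Other stronger readings also go too far:

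- Eighteen might be read as the most that can be lost. It is the planned allowance; actual loss could be larger or smaller.
- One might say that everyone who leaves is dropped. PDA and DPDD are summaries over days, so someone who reports Days 8 to 10 has a computable PDA. The plan does not say whether partial weeks count or how the repeated factor is built.
- One might say that TLFB data from all early leavers would be discarded. No visit is described between Day 1 and Day 8, so a participant who leaves during titration and does not return may have no post-randomisation TLFB data at all.
- One might take bias as certain. It requires dropout that differs by arm in amount or in its link to drinking.

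The design also limits loss: dosing lasts 14 days, contact is daily in the quit week, and there are visit payments, transport and a $50 bonus.

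What remains is that the named method deletes incomplete records and the plan offers nothing in its place. The open question about partial weeks is part of that gap.

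**Conclusion.** The point holds as a defect in the planned analysis that should be corrected. It does not show that the trial will exclude people or that its result will be biased. The plan sizes on completers, is silent on the analysis population and missing data, and names a method that deletes incomplete records, so a complete-case comparison is what it leads to by default.

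The possible size is modest but not negligible: 2.7 to 5.3 PDA points in the main illustration, or 0.09 to 0.30 SD in the second model where dropout differs by arm. All of these rest on assumed dropout splits, PDA gaps and correlations that the documents neither support nor rule out.

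**What to change.** State that Aims 1 and 2 are analysed in all randomised participants as assigned, and keep 90 completers only as the sizing assumption.

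- **Aim 1:** replace PROC GLM with a likelihood-based mixed model that uses every reported TLFB day. Use multiple imputation from baseline drinking for those with no quit-week data. Add one sensitivity analysis for PDA that counts missing quit days as drinking days. That rule assigns no quantity, so for DPDD impute the amount, for example from baseline DPDD.
- **Aim 2:** TLFB data cannot help here. Fit a mixed model to the Day 1 and Day 14 AUQ alcohol-minus-water scores, so that participants missing Day 14 still contribute their Day 1 score.

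The mixed models and imputation assume that missingness is explained by the observed data. The sensitivity analysis is there because that may fail for PDA.

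The cost is SAP wording and a modest amount of extra analysis, with no added participants or visits. The downside is possible dilution of the effect: power of 0.873 in the no-effect case above, against 0.926 for 90 completers.

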### **3.2. Data Analytic Plan**

Descriptive statistics will be computed for continuous outcome variables, and frequencies for categorical variables to summarize the study data. Box plots, histograms, and Q-Q plots will be used to check for skewness and normality for continuous variables. Transformations of continuous outcome variables will be performed as necessary to ensure that the normality assumptions in parametric tests are met. The models described below will test whether medication effects in reducing drinking behavior during the practice quit attempt are associated with concurrent blunting of cue reactivity. To improve model fit and hypothesis testing, we will consider covariates, such as age, sex, ethnicity, medication order, and AUD symptom count.

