### 5.4. Medication Phase

#### 5.4.1. Randomization and Medication Titration

Participants who are eligible after the physical exam will be randomized to one of three treatment conditions (VAR, NTX, or PLA). Urn randomization will be used to balance the groups by gender, smoking status (as reported on question 1 of the Fagerstrom Test for Nicotine Dependence), and drinking status ('heavy' drinker defined as 14 or more drinks per week for

males/7 or more drinks per week for females, or 'very heavy' drinker, defined as 35 or more drinks per week for males/28 or more drinks per week for females). The UCLA Research Pharmacy will manage the blind. The three treatment conditions will not be different in appearance or method of administration. All participants will undergo a week-long medication titration period prior to the onset of the practice quit attempt.

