#### **3.2.2. Primary Aim 2: To test that NTX and VAR will reduce cue-induced craving for alcohol as compared to placebo.**

We will conduct a series of repeated measures ANOVAs on Alcohol Cue – Water Cue change scores on the AUQ as predicted by Medication condition (NTX vs. PLAC and VAR vs. PLAC).

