#### **3.2.4. Secondary Aim 1: Medication Effects on Alcohol Choice, Delay Discounting, and Alcohol Demand.**

One-way Analysis of Covariance (ANCOVAs) will be used to determine significant mean differences in crossover points on the multiple-choice paradigm, delay discounting, and alcohol demand between the medication groups (naltrexone, varenicline, and placebo). Mediation analyses will be used to determine whether the effects of medication on the multiple-choice paradigm were mediated by changes in discounting or demand for alcohol. Baseline covariates such as age, sex, and smoking status will be included in the model.

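### The Aim 1 and Aim 2 models commit to none of the urn balancing factors, and the optional covariate list has no selection rule and includes a medication-order term that a parallel-group trial cannot have

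*Combined protocol and SAP*

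**What the plan says.** Section 5.4.1 (Randomization and Medication Titration): "Urn randomization will be used to balance the groups by gender, smoking status" (taken from question 1 of the Fagerstrom test) "and drinking status ('heavy' drinker defined as 14 or more drinks per week for" men or 7 or more for women, against a very heavy category starting at 35 and 28 drinks per week.

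Section 3.2 (Data Analytic Plan), with the stated purpose of improving model fit and hypothesis testing: "we will consider covariates, such as age, sex, ethnicity, medication order, and AUD symptom count".

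Section 3.2.1 (Primary Aim 1) models PDA and DPDD "as predicted by Medication (NTX vs. PLAC and VAR vs. PLAC) a between-subjects factor and the covariate of baseline PDA and DPDD".

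Section 3.2.2 (Primary Aim 2) models alcohol-minus-water "change scores on the AUQ as predicted by Medication condition (NTX vs. PLAC and VAR vs. PLAC"), with no covariate named.

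Section 3.2.4 (Secondary Aim 1): "Baseline covariates such as age, sex, and smoking status will be included in the model". Section 3.2.5 makes the same commitment for Secondary Aim 2.

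Section 4.1 (Design Overview) describes a "randomized, double-blind, placebo-controlled, 3-arm, parallel-group study of naltrexone (50 mg QD) and varenicline (1 mg BID").

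**The concern.** A factor chosen for balancing is normally one expected to predict outcome, and the analysis should then contain it. Here neither primary model commits to any of the three. Smoking status appears in neither primary model nor in the optional list, yet both secondary analyses include it, and no reason is given for the difference.

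The sentence meant to settle the covariates does not do so. It is worded as something to be considered, gives examples rather than a closed list, and has no rule for what enters a model. One of its five items, medication order, has no meaning when each participant receives a single treatment.

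Two things are at stake. The primary comparisons lose some precision, in a trial whose purpose is to detect an early efficacy signal. And the adjustment set behind the primary result is not fixed in advance.

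**Working it through.** **1. Terms side by side.**

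| Factor | Urn (5.4.1) | Aim 1 (3.2.1) | Aim 2 (3.2.2) | Optional list (3.2) | Secondary (3.2.4, 3.2.5) |
|---|---|---|---|---|---|
| Gender/sex | yes | no | no | yes | yes |
| Smoking status | yes | no | no | no | yes |
| Drinking status | yes | through baseline PDA and DPDD | no | no | not named |
| Medication order | – | no | no | yes | no |

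The dosing table in 5.4.3.1 gives each arm one regimen, so medication order would have no values to enter. The NTX – PLAC and VAR – PLAC change scores in 3.2.3 also read like crossover language.

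**2. The plan's own power figure.** Inputs from section 3.1 (Statistical Power): one-way ANOVA, 3 groups, 90 completers, f = 0.40, alpha 0.05, stated power 0.91 (printed with a stray percent sign). Noncentral F with λ = N f² = 90 × 0.16 = 14.4 on 2 and 87 df gives 0.926, within two points of the stated figure (N = 84 gives 0.907). Dropout: 90/(1 − 1/6) = 108, as planned.

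**3. Power after adjustment.** Let R² be the share of within-arm outcome variance explained by the three factors. The documents give no value, so 0.10 and 0.20 are assumptions. With three binary factors, λ becomes N f²/(1 − R²) and error df fall to 84.

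| R² | λ at f = 0.40 | Power | λ at f = 0.25 (assumed) | Power |
|---|---|---|---|---|
| 0 | 14.4 | 0.926 | 5.63 | 0.539 |
| 0.10 | 14.4/0.9 = 16.0 | 0.950 | 5.625/0.9 = 6.25 | 0.586 |
| 0.20 | 14.4/0.8 = 18.0 | 0.970 | 5.625/0.8 = 7.03 | 0.641 |

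The first row shows that the three df cost almost nothing if the factors turn out not to be prognostic. A simulation with urn allocation of 90 (3,000 runs per scenario) compared the analysis without and with the factors. At f = 0.25 it gave 0.538 and 0.589 (R² = 0.10), then 0.541 and 0.622 (R² = 0.20). At f = 0.40 it gave 0.927 and 0.951, then 0.920 and 0.959. The formula is therefore slightly optimistic at R² = 0.20.

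**4. Type I error when the factors are left out (nominal 5%).**

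| Allocation simulated | R² = 0.10 | R² = 0.20 |
|---|---|---|
| Urn, 90 analysed, omnibus test (Monte Carlo SE about 0.4 points) | 5.1% | 3.5% |
| Urn allocation of 108, random loss to 90 | about 4.7% | about 4.2% |
| As above, pairwise contrast (SE about 0.3 points) | 4.6% | 3.8% |
| Perfect balance on one binary factor, 30 per arm | 3.7% | 2.9% |

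The middle rows are closest to this trial, because an urn balances only approximately and section 3.1 plans for 18 of 108 to be lost. They give about 4% to 5%. None of the results points to inflation. Factor prevalences (40%, 40% and 35% in the first simulation), equal factor effects and the exact urn rule are assumptions.

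**5. Overlap in Aim 1.** With PDA as a proportion, weekly drinks = 7 × (1 − PDA) × DPDD. The urn drinking category is a sex-specific cut of that quantity, so baseline PDA and DPDD already carry much of it. The gap in Aim 1 is mainly smoking status, and sex as a committed term.

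**The case against.** Several counter-arguments have force.

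- At the planned f = 0.40 the gain is only about 2 to 4 points on power that is already above 0.9. This is right; the gain matters mainly if effects are smaller. Section 2.4 itself describes naltrexone effect sizes as often modest.
- In Aim 1 the remaining R² is probably below the 10% to 20% used above, because of the overlap in step 5. In Aim 2, if the Day 1 and Day 14 sessions form the repeated factor (3.2.2 does not say), the medication-by-session test already removes stable differences between people. Both points stand and make the gains above upper-end figures.
- Sex is on the optional list, and the list is open, so smoking status is not ruled out. This is true, but nothing commits the primary models to either.

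Three stronger readings are tempting and are not supported.

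- A reader might infer that leaving out the factors raises the false-positive rate. It does not; the effect runs the other way.
- A reader might infer marked conservatism, near 3%. That needs perfect balance, which an urn with dropout does not give.
- A reader might infer that covariates will be picked after outcomes are seen. Section 3.2 states no timing. Its purpose clause leaves that possible, but the documents do not say it will happen.

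Finally, the fact that varenicline is a smoking-cessation drug bears on effect modification by smoking. A main-effect covariate does not address that, so it is not the reason for the change. The reason is that the sponsor chose to balance on smoking status.

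**Conclusion.** The point holds as one of lost precision and an unfixed adjustment set. The primary models commit to none of the urn factors, the covariate sentence contains a term that cannot be fitted, and the secondary models are better specified than the primary ones. These findings come from the text alone and need no assumption.

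The size is modest and rests on an assumed R² of 0.10 to 0.20. The unadjusted test is mildly conservative, and the power gain is a few points at the planned effect and roughly 5 to 10 points at f = 0.25, less where baseline drinking or a repeated session factor already does the work. The planned sample size is not called into question.

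**What to change.** - **Section 3.2.1:** prespecify gender and smoking status as fixed covariates alongside baseline PDA and DPDD. The urn drinking category may be added for consistency with the randomisation, but it is largely redundant.
- **Section 3.2.2:** prespecify gender, smoking status and drinking status (the urn category or continuous baseline drinking). State whether session is the repeated factor. If Day 14 is analysed as the outcome, include the Day 1 alcohol-minus-water AUQ score as the baseline covariate.
- **Section 3.2:** delete medication order, and limit the other listed covariates (age, ethnicity, AUD symptom count) to named sensitivity analyses.

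The cost is a few sentences in the analysis plan and about three error degrees of freedom. At N = 90 and f = 0.40 those three df leave power at 0.926 even if the factors explain nothing. All the variables are already collected: the urn needs gender, smoking status and drinking status before allocation, and the Day 1 cue session supplies the AUQ baseline.
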